3.1 Primary outcome

Fasting plasma copeptin (measured at baseline and at 6 weeks).

3.2 Secondary outcomes

24 hour urine osmolality (measured at baseline, at 3 weeks and at 6 weeks).

24 hour urine volume (measured at baseline, at 3 weeks and at 6 weeks).

Drinking water (measured at baseline and at 6 weeks).

Total water (measured at baseline and at 6 weeks).

Fasting plasma glucose concentration (measured at baseline, at 3 weeks and at 6 weeks).

Surveys

Health-related quality of life, fluid/water and dietary intake (using Riksmaten 2010), stool form (Bristol Stool Scale).

3.3 Safety outcomes

Adverse events

Adverse events are reported at each clinic visit.

Concomitant medications

Usage of medications during study period will be recorded.

4. Populations and subgroups to be analysed

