Weight (Kg)			+		+
Waist circumference (cm)			+		+
Blood pressure (mm Hg)			+		+
Medications			+		+
BLOOD					
Blood sample	+		+	+	+
Fasting glucose (mmol/L)			+		+
Oral glucose tolerance test (OGTT) (mmol/L)			+		+
Fasting and 2h insulin (during OGTT) (mIE/L)			+		+
Fasting and 2h glucagon during OGTT (pmol/L)			+		+
Fasting cortisol (nmol/L)			+		+
Fasting ACTH (pmol/L)			+		+
Fasting copeptin (pmol/L)			+		+
Fasting Lipids/lipoproteins ^d (mmol/L)/(g/L)			+		+
C-reactive protein (mg/L)			+		+
Creatinine (μmol/L)	+		+	+	+
eGFR (mL/min/1,73 m ²)	+		+		+
Sodium (mmol/L)	+		+	+	+
Potassium (mmol/L)			+	+	+
Urea (mmol/L)			+	+	+
Osmolality (mOsm/kg)			+	+	+
Erythrocyte Volume Fraction (%)			+		+
HbA1c (mmol/mol)			+		+
Plasma samples for long term storage			+		+
Whole blood for DNA isolation			+		
URINE					
24-hour urine sample		+		+	+
Urine volume (ml)		+		+	+
Creatinine (mmol/24h)		+		+	+

Sodium (mmol/24h)		+		+	+
Potassium (mmol/24h)		+		+	+
Urea (mmol/24h)		+		+	+
Osmolality (mOsm/kg)		+		+	+
Albumin/creatinine ratio (g/mol)		+			+
Cortisol (nmol/24h)		+			+
Urine for long term storage		+			+
FAECES					
Sample for microbiome seq			+		+
Bristol stool score			+		+
Check for adverse events				+	+

^aPre-intervention.
^bTime after baseline.
^cIn addition to coaching during telephone contacts.
^dtriglycerides, LDL, HDL, ApoA1, ApoB.

Protocol: All visits will take place at Skåne University Hospital. Recruitment and intervention will be ongoing from February to August 2017 (rolling enrollment, 6 weeks follow up).

Coaching and enquire about adherence and tolerance to water treatment will take place both during clinical visits after baseline, and during telephone contacts (Table 1, Figure 1) to optimize compliance. Color charts will be used at all telephone contacts, and measures of urine volume and urine osmolality will be used at clinical visits, to motivate the participants to increase their water supplementation/compliance if lack of compliance is indicated, suspected or documented based on these parameters.

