Clinic visits will be performed at baseline, after 3 weeks of intervention and after 6 weeks (i.e. at the end of the intervention). For the sequence of events during visits please see Table 1. Between visits, telephone contacts will be scheduled for coaching (Figure 1). At baseline, and at the end of the water intervention, plasma copeptin, electrolytes, C-reactive protein and fasting glucose will be measured, anthropometry will be assessed, and 24h urine will be collected. Furthermore, current medication and medical history will be recorded, and fluid/water and dietary intake will be assessed using “Riksmaten 2010”, a validated web-based 4-day record tool developed by the Swedish National Food Administration and used in the latest national diet survey in Swedish adults (*J Nutr Sci* 2016,5:e39). In addition to Riksmaten recording, participants will fill in a food propensity questionnaire to assess foods that may not be consumed within the 4 days (like fish, berries or sugar-sweetened beverages). To help with the registration, participants will receive a food/drink dairy and a portion guide with pictures of 24 different food categories. In addition, there is an instruction video available via YouTube <https://www.youtube.com/watch?v=DB3bzD0FJMg>. Blood pressure will be measured after a 5-minute rest. At the 3-week visit, plasma electrolytes will be measured, and 24h urine will be collected for measurement of urine volume and urine osmolality. These measures will, together with urine color charts, be used to motivate the participants to keep up or, in case of indications of lack of compliance, increase their water intake.

Laboratory measurements: All plasma laboratory analyses (Table 1), except copeptin, will be performed using certified methods at the Skane University Hospital’s central clinical lab. Plasma copeptin will be measured in our lab in fasting plasma samples stored at -80°C using a

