The aim of this study is to perform a pilot study in 30 subjects, before the start of a long term RCT. Thus, we have not performed a power calculation. In the study we will test for the first time if six weeks of moderate water supplementation (1.5L extra water per day) in low-drinkers with high plasma levels of copeptin can significantly reduce plasma copeptin concentration. The primary outcome measure of the study is the change of fasting plasma copeptin between baseline and 6 weeks of water intervention. Furthermore, the study is designed to investigate study logistics, safety, compliance and drop-out rate before the start of a long term (1 year) RCT. Finally, as fasting plasma glucose will be the primary endpoint of the long term RCT, we also aim at investigating whether the 6-week water intervention can significantly reduce fasting plasma glucose concentration.

2. Sample size

A pilot study with 30 participants.

3. Outcomes

This section will present the outcomes investigated to answer the study aims and objectives. The analyses are described in section 5 Analyses.

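### Adverse events are scheduled for collection only at the week-3 and week-6 visits, although tolerance is already asked by telephone, so a participant who leaves before week 3 has no planned safety record

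*Combined protocol and SAP*

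**What the plan says.** Safety is among the purposes of the pilot. SAP section 1 states that "the study is designed to investigate study logistics, safety, compliance and drop-out rate before the start of a long term (1 year) RCT".

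The collection rule is one sentence in SAP 3.3: "Adverse events are reported at each clinic visit". The protocol fixes when those visits fall: "Clinic visits will be performed at baseline, after 3 weeks of intervention and after 6 weeks". In Table 1 the row "Check for adverse events" is marked in the 3-week and 6-week columns and nowhere else. The table has no column for telephone contacts.

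The Protocol paragraph under Project Design adds that coaching and the duty to "enquire about adherence and tolerance to water treatment will take place both during clinical visits after baseline, and during telephone contacts". Its stated purpose is better compliance. The description of the clinic visits likewise gives coaching as the reason for the calls between visits, and refers to Figure 1 for them (the figure is not available here).

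SAP 4.1 names one analysis population, the participants who complete the whole study period. No separate safety population is defined. Neither document says how adverse events are obtained from someone who leaves before a scheduled check.

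**The concern.** The first planned adverse-event check after the water starts comes three weeks into a six-week intervention. Before then, the only planned question about how participants tolerate the water is asked by telephone, and the plan gives that answer no route into the safety data.

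Two things follow if the rule is applied as written. A participant who leaves before the week-3 visit contributes nothing to the adverse-event record. For those who stay, mild early symptoms are captured only if they are remembered for up to three weeks.

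The pilot is meant to inform a one-year RCT. Poor tolerance soon after starting is a plausible reason for leaving early, and it is information the longer trial would need. If that is why people leave, the safety aim is under-measured where it matters most.

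The completer population adds a second, separate loss. If adverse events are summarised in completers only, an event recorded at week 3 in someone who leaves before week 6 would also disappear from the summary. A wider analysis set would restore that event. It could not restore one that was never recorded.

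**Working it through.** The plan states no adverse-event rate, precision target or expected drop-out for this point, so there is no figure of its own to reproduce. SAP section 2 gives only "A pilot study with 30 participants", and section 1 says "Thus, we have not performed a power calculation". The check is therefore a reading of the passages, followed by an illustration on assumed losses.

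**1. Contacts and what is collected at each**

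| Contact | Tolerance asked? | Adverse-event check planned? |
|---|---|---|
| Baseline (water starts) | no | no |
| Telephone contacts between visits | yes | not stated |
| Week 3 | yes | yes |
| Week 6 | yes | yes |

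The telephone row is the gap. The first planned check comes at 3 × 7 = 21 of 6 × 7 = 42 days. Those 21 days are not lost for people who attend week 3, because they are asked then. They are lost for people who leave before it.

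**2. Illustration with no events seen at the visits**

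Inputs: n = 30 (SAP section 2); d = participants who leave before week 3. The documents do not give d, so 1, 3 and 6 are assumed. The exact two-sided 95% upper limit for 0 events in m = 30 − d is 1 − 0.025^(1/m). The last column assumes that all d left because of an event.

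| d | Visits show | Exact 95% CI | Proportion of all 30 |
|---|---|---|---|
| 1 | 0/29 | 0 to 11.9% | 1/30 = 3.3% |
| 3 | 0/27 | 0 to 12.8% | 3/30 = 10.0% |
| 6 | 0/24 | 0 to 14.2% | 6/30 = 20.0% |

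For d = 3: 1 − 0.025^(1/27) = 0.1277. The proportions in the last column are minimum values, since participants who stayed could also have had events that they did not recall.

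**3. Illustration with 3 participants with events among those seen**

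The low end is 3/30 (none of the d had an event). The high end is (3 + d)/30 (all of them did).

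| d | Observed | Range over all 30 |
|---|---|---|
| 1 | 3/29 = 10.3% | 10.0% to 13.3% |
| 3 | 3/27 = 11.1% | 10.0% to 20.0% |
| 6 | 3/24 = 12.5% | 10.0% to 30.0% |

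The direction depends on why people leave. If none of the leavers had an event, the observed rate is slightly too high (11.1% against 10.0% at d = 3).

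**4. How likely is at least one early loss?**

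For an assumed probability p per participant, the chance is 1 − (1 − p)^30. This gives 78.5% at p = 5%, 95.8% at p = 10% and 99.9% at p = 20%.

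**The case against.** The sponsor can answer on several grounds.

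- **Stopping the water is not leaving the study.** A reader might infer that anyone who stops before week 3 has no adverse-event record. The documents do not support that. Nothing says that such a participant is withdrawn or misses the visit, and someone who stops and still attends week 3 is checked there. The missing record concerns early leavers only.
- **The plan does not forbid recording events reported by telephone.** This is correct. Table 1 lists visits and has no telephone column, and Figure 1 is not available here. It remains true that the only collection rule in the text names clinic visits, and that no text connects the telephone question to the adverse-event record.
- **The data-handling list proves nothing.** A reader might take the absence of telephone answers from the protocol's Data handling paragraph as evidence that they are not stored. That list does not name adverse events from clinic visits either, so it is not exhaustive and carries no weight here.
- **The safety result need not be too favourable.** A reader might conclude that it must be. As step 3 shows, this depends on why people leave, which the documents cannot tell us.
- **The numbers are assumed, and the interval covers the hidden rate.** Both are true: the interval for 0 of 27 contains 10%. The illustration does not show a statistically detectable bias. It shows that a report of no events would be compatible with three people having left because of them.
- **Early leavers would show up in the drop-out rate.** They would be counted, but the plan provides for no record of an adverse event as the cause.
- **Three-weekly enquiry is a defensible choice in a small, short pilot, and week 3 includes blood chemistry.** This is fair for those who attend. It does not help for those who do not.

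These points limit the concern to early leavers and to recall. They do not remove it.

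**Conclusion.** The point holds in this limited form and is a cheap improvement. The planned adverse-event checks fall only at weeks 3 and 6, while a tolerance question already asked by telephone is not linked to the safety record. Applied literally, the rule leaves participants who leave before week 3 without an adverse-event record and makes early mild symptoms depend on recall.

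The effect on the safety result cannot be sized from the documents. It rests on three unknowns: how many leave before week 3, whether they leave because of intolerance, and whether staff would in practice record what they hear by telephone. With 30 participants, each unrecorded participant with an event lowers the count by 1/30 = 3.3 percentage points.

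**What to change.** 1. Replace the sentence in SAP 3.3 with: *Adverse events are recorded at each clinic visit, at each scheduled telephone contact, and when a participant stops the water or leaves the study.*
2. Carry this into Table 1. A footnote is enough, as is already done there for coaching by telephone.
3. Enter the event, its onset date, and the reason for stopping or leaving in the eCRF.
4. State in SAP section 4 or 5 that adverse events are summarised in all participants who started the water, not in completers only.

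The cost is one short form and a few minutes per call, on calls already scheduled and a question already asked. No extra visit is needed. Participants who cannot be reached by telephone would still be missing, and the report should give their number.

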The aim of this study is to perform a pilot study to test if six weeks of moderate water supplementation of 1.5L extra water per day in low-drinkers with high plasma levels of VP can significantly alter hydration markers in general and reduce plasma VP (measured as the stable VP marker copeptin) in particular. The study was also designed to investigate study logistics, safety, compliance and drop-out rate before the start of a long term (1 year) RCT. Furthermore, as fasting plasma glucose will be the primary endpoint of the long term RCT, we also aim at investigating whether the 6-week water intervention can significantly reduce fasting plasma glucose concentration.

SURVEY OF THE FIELD

The main physiological role of VP is to maintain constant plasma osmolality. When water intake is low, increased pituitary VP secretion prevents hyper-osmolality by enhancing renal water reabsorption through VP stimulation of the V2-receptor in the renal collecting ducts, whereas at higher levels of water intake, VP secretion is suppressed and circulating VP is low. Another effect of VP is that it increases release of adrenocorticotropic hormone (ACTH) through binding to the VP-1B receptor in the pituitary gland and thereby leads to elevated adrenal cortisol secretion and a Cushing's syndrome-like phenotype, i.e. diabetes, insulin

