Population: We previously showed that subjects with high VP (i.e. copeptin of >6.1 pmol/L in women and >10.7 pmol/L in men), which corresponds to 25% of the population aged 20-75y, has 3-4 times elevated risk for diabetes development, i.e. a magnitude of risk that is similar to that of obesity, and a doubled risk of CVD mortality. In addition, the high VP target group of this study has a urine osmolality of >600 mosm/kg water, i.e. concentrated urine concordant with a low water intake.

[figure not shown]
Screening and inclusion process: Study subjects (n=30) will be recruited from the Malmö Offspring Study (n=1547) (<http://www.med.lu.se/mos>). Copeptin will be measured in -80 degree frozen plasma samples from this study. Assuming that the prevalence of having high plasma copeptin concentration of >6.1 pmol/L in women and >10.7 pmol/L in men will be approximately 25%, around 400 individuals will have high copeptin concentrations and will be eligible for the current study. These individuals will be contacted by letter and subsequently by telephone. Individuals interested in participation, who do not have any medication or disease implying immediate exclusion (see inclusion and exclusion criteria below), will be invited to participate in the current study.

Inclusion criteria will be provision of informed consent, age 20-75 years with high plasma concentration of VP (plasma concentration of copeptin of >6.1 pmol/L in women and >10.7 pmol/L in men) and 24-hour urine osmolality ≥ 600 mosm/kg water.

Exclusion criteria will be 24-hour urine volume >1.5 L, pregnancy or breastfeeding, plasma sodium <135 mM, use of diuretics, lithium or SSRI drugs, chronic kidney disease (eGFR <30 mL/min), heart failure, inflammatory bowel disease, type 1 diabetes or type 2

diabetes treated with insulin and vulnerable subjects (subjects with legal guardian, with loss of personal liberty).

Figure 1. Study protocol

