Intervention: All participants will be instructed to add 1.5 L of plain water daily on the top of habitual intake (intervention) during six weeks (Figure 1). At baseline, all participants also will receive general oral and written advice on diet and physical activity. Adherence to high water intake will be achieved by coaching at the clinic visit and by regular telephone contacts with the participants. We benefit from shared experience of how to successfully perform the water intervention by collaboration with [name], London Health Science Centre, Canada (co-investigator in current project) who is PI of the Chronic Kidney Disease Water Intervention Trial (WIT) (same water vs control intervention as in current study but primary outcome = effect of water on decline of GFR) whose Data Safety Monitoring Report was completed June 2015 and showed excellent separation in water intake during follow-up (measured by 24-hour urine volume) and safety. In accordance with the protocol of the WIT, adherence to high water intake will be achieved by coaching at the clinic visits and by regular telephone contacts. Furthermore, we will provide urine color charts to use at home to facilitate adherence to target urine concentration.

Outcome: We will test if six weeks of water supplementation of 1.5L extra water per day in low-drinkers with high copeptin significantly alter hydration markers in general and reduce plasma copeptin in particular. Furthermore, as fasting plasma glucose will be the primary endpoint of the long term RCT, we will also investigate whether the 6-week water intervention could significantly reduce fasting plasma glucose concentration. Significance of differences between baseline and after intervention will be tested using paired t-test or Wilcoxon's paired rank test depending on distribution. SPSS statistical software version 24 (SPSS Inc., Chicago, Ill., USA) will be used for all analyses. A 2-sided p value of <0.05 will be considered statistically significant.

Table 1. Schedule of visits and measures

				Follow-up ^b
--	--	--	--	-------------------------------

	Visit 1 ^{a,c}	Visit 2 (Inclusion) ^{a,c}	Baseline (Week 0)	3 weeks	6 weeks
Informed Consent Process and Informed Consent Form Signature	+				
Exclusion criteria check-up including pregnancy	+				
SURVEY					
Demographics			+		
Diet (4-day report)			+		+
Health history			+		+
Health-related quality of life			+		+
Hydration coaching ^c			+	+	+
CLINICAL					
Height (cm)			+		+

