4.1 Populations

Per Protocol (PP)

All included study subjects completing the whole study period (complete cases) will be seen as the primary population for the analysis. For a specific analysis, study subjects with missing data on any of the variables in the model will be excluded from the analysis.

5. Analyses

All outcomes will be presented using descriptive statistics; normally distributed data by the mean and standard deviation (SD) and skewed distributions by the median and interquartile range (IQR). Binary and categorical variables will be presented using counts and percentages. SPSS statistical software version 24 (SPSS Inc., Chicago, Ill., USA) will be used for all statistical analysis.

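### Safety is a stated aim and plasma sodium is measured at baseline, 3 and 6 weeks, but the SAP plans no use of sodium and gives early stoppers no defined place in the safety reporting

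*Combined protocol and SAP*

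**What the plan says.** **Aim.** The protocol's statement of aims says: "The study was also designed to investigate study logistics, safety, compliance and drop-out rate". SAP section 1 repeats it: "the study is designed to investigate study logistics, safety, compliance and drop-out rate". Both place this ahead of a 1-year RCT.

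**Intervention.** Under Intervention: "All participants will be instructed to add 1.5 L of plain water daily on the top of habitual intake".

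**Measurement.** Table 1 marks plasma sodium at Visit 1, baseline, 3 weeks and 6 weeks, the same four columns as the blood sample row. The text under Protocol agrees. For baseline and the end of the intervention it says "plasma copeptin, electrolytes, C-reactive protein and fasting glucose will be measured", and for the visit between them "At the 3-week visit, plasma electrolytes will be measured".

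**Entry limit.** The exclusion criteria include "plasma sodium <135 mM". No reason is given, and no sodium limit is stated for any later visit.

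**Safety outcomes.** SAP 3.3 has two items. The first is adverse events: "Adverse events are reported at each clinic visit". The second is the recording of medication use.

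**Population.** SAP 4.1 defines one population: "All included study subjects completing the whole study period (complete cases) will be seen as the primary population for the analysis".

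**The concern.** Safety is one of the things the pilot is meant to establish, and a laboratory value that bears on added plain water is already being collected twice during the intervention. The SAP makes no use of it. The safety result then consists of adverse events, for which no definition is given, and a medication record.

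Two kinds of information may be lost. A fall in sodium without symptoms, or an average fall that stays above any limit, is something that event counting is poorly suited to show. Participants who stop because they tolerate the water badly are the most informative for safety, and the only population in the SAP is people who finished.

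At stake is what the team planning the 1-year RCT can conclude from the pilot. Without a pre-stated summary, whether and how sodium is reported will be decided after the values are known.

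**Working it through.** The plan states no figure to reproduce: the sample size of 30 was set without a power calculation, and no expected sodium change or event rate is given. The check is a comparison of schedule with analysis, followed by an illustration.

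**Step 1. Follow sodium through the documents.**

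| Place | Plasma sodium |
|---|---|
| Protocol, exclusion criteria | Limit of 135 mM, at entry only |
| Protocol, Table 1 | Visit 1, baseline, 3 weeks, 6 weeks (4 of 4 blood-sampling visits, 2 after baseline) |
| SAP 3.1, primary outcome | Not named (copeptin) |
| SAP 3.2, secondary outcomes | Not named (urine osmolality, urine volume, drinking water, total water, fasting glucose, surveys) |
| SAP 3.3, safety outcomes | Not named |
| SAP 5.1 and 5.2, analyses | Not named |

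The opening of SAP section 5 promises descriptive statistics for all outcomes. Sodium is not a listed outcome, so that promise does not reach it. Section 5 has subsections for primary and secondary outcomes and none for safety.

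**Step 2. Look for a rule that turns a sodium value into a safety finding.** There is no adverse event definition, no laboratory threshold after baseline and no reporting rule. The one use the protocol gives for the 3-week measures is to encourage participants to maintain or raise their water intake.

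**Step 3. Look for a place for early stoppers.** SAP 4.1 names completers as the primary population and defines no other. Neither 3.3 nor section 5 says in whom adverse events are to be reported.

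**Step 4. What a sodium summary in 30 people could say (illustration; the counts are hypothetical).** The exact (Clopper-Pearson) two-sided 95% interval for x cases in n has a lower limit p solving P(X ≥ x | n, p) = 0.025 and an upper limit solving P(X ≤ x | n, p) = 0.025. For x = 0 the upper limit reduces to 1 − 0.025^(1/n).

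- n = 30, x = 0: 1 − 0.025^(1/30) = 0.116, so 0 to 11.6%
- n = 30, x = 1: 0.1 to 17.2%
- n = 30, x = 2: 0.8 to 22.1%

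If only completers were counted and 27 or 24 finished (assumed numbers), the upper limit for x = 0 would be 1 − 0.025^(1/27) = 12.8% or 1 − 0.025^(1/24) = 14.2%. The loss of precision is small. The larger worry is who would be missing.

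The chance of seeing at least one case in 30 is 1 − (1 − p)^30. For assumed true rates of 1%, 2%, 5% and 10% it is 26%, 46%, 79% and 96%. An absence of cases would therefore be weak reassurance about rates of 1% or 2%, which is a reason to report the interval as well as the count.

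**The case against.** The strongest points on the other side are these.

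- **A low sodium could still be reported.** Adverse events are not limited to symptoms. Routine chemistry is analysed directly during the trial and hospital laboratory results are imported into the study database, so the site would have the value. This stands. A reader might infer that a symptomless fall is certain to be absent from the safety conclusion, and the documents do not support that. They show that nothing requires it to be included.
- **The purpose of the sodium measurement is not stated.** The protocol gives no reason for the sodium exclusion or for the exclusions of diuretics, lithium and SSRIs, and no safety purpose for the electrolytes. A reader might infer that the protocol identifies low sodium as the hazard of the intervention. The entry limit suggests this but does not say it.
- **The protocol aims to test hydration markers broadly, with paired tests.** Plasma sodium might fall under that phrase. But the SAP turns it into four named variables (urine osmolality, urine volume, drinking water and total water) and does not carry sodium over, so this is not a pre-specified sodium outcome.
- **Completers are called the primary population, not the only one allowed.** Adverse events are checked at week 3, before anyone has completed, and drop-out is itself an aim. A reader might infer that early stoppers are excluded from safety reporting, but the SAP does not say so. What stands is that no safety population is defined.
- **This is a small single-arm pilot.** A sodium table would be descriptive, and even a clean one would leave wide limits. That is correct, and it limits the weight of the point. It does not remove it, because safety is one of the pilot's stated aims.

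**Conclusion.** The point holds as a gap in the safety reporting plan. Sodium is measured at two visits after baseline and appears in no SAP outcome and no SAP analysis. Its entry into the safety result depends on someone choosing to record a value as an adverse event. Participants who stop early have no defined place.

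The consequence for the pilot's conclusion cannot be quantified: the documents give neither an expected sodium change nor an event rate, and the figure of 0 to 11.6% for 0 of 30 shows only the precision available. The conclusion rests on reading Table 1 as printed and on the absence of any adverse event definition in the protocol or SAP.

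The primary copeptin analysis is not affected. The change is still worth making before the data are analysed, because it costs almost nothing and one of the study's aims otherwise lacks a directly relevant laboratory measure that is already being collected. Nothing here bears on how a low value should be managed.

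**What to change.** 1. **Add plasma sodium to SAP 3.3.** Suggested content: change from the baseline visit to 3 weeks and to 6 weeks, as a mean with 95% CI; the lowest post-baseline value; and the number and proportion below a pre-stated descriptive limit, with exact 95% CI. The protocol's own entry limit of 135 mM is one candidate; the choice is the sponsor's. Analyse all participants who started the intervention and have a post-baseline value, and state how many have none. That last count matters because anyone who stops before week 3 may have no sodium value during the intervention.

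2. **Add a safety set to SAP 4.1:** all participants who started the intervention. Report adverse events in this set, not only in completers.

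3. **Add a short safety subsection to SAP section 5** stating that these summaries are descriptive.

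The cost is a few lines of SAP text and one small table. Sodium is already scheduled, so no extra samples or visits are needed. No clinical rule is proposed, and the limit serves only to describe the data.
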